# Objective:

1. To test the performance of the wearable SDD (NightWatch) prospectively and the remote SDD (automated video and audio analysis) retrospectively in children in a family home setting. 2. To assess the feasibility, cost-effectiveness and cost-utility of NightWatch in children.

**Study design:** A multicenter home-based medical device intervention study with prospective validation of our wearable SDD.

**Study population:** 60 children (ages 4-16 years) with refractory epilepsy (≥1 major nocturnal seizure per week) recruited from the outpatient clinics of one of the participating epilepsy centers (Stichting Epilepsie instellingen Nederland (SEIN), Academic Centre of Epileptology Kempenhaeghe (Kempenhaeghe), University Medical Center Utrecht (UMCU)).

**Intervention (if applicable)**: Phase I: Two months of baseline (usual care); Phase 2: Two months of nocturnal seizure monitoring at home, using NightWatch and the remote SDD.

Main study parameters/endpoints: The diagnostic performance of NightWatch and the remote SDD algorithms, i.e. sensitivity, positive predictive value, false alarm rate and % time with uninterrupted signal output. We will evaluate feasibility of NightWatch through surveys on quality of life, sleep, parental strain, interviews with parents/guardians and neurologists, and a value sensitive design group session. We will also perform a cost-effectiveness and cost-utility analysis by medical consumption and costs questionnaires.

Nature and extent of the burden and risks associated with participation, benefit and group relatedness: Implementing SDDs will not pose any direct or substantial risk. Study participation can be a burden though, due to impact of the devices on privacy, number of false alarms and time spent on the questionnaires and interviews. Application of the SDDs, however, might offer better insight into the actual number of nocturnal seizures in a child, change in medical management and facilitate appropriate interventions in major motor seizures. If reliable, SDDs may improve the night rest of both patient and parents/guardians.

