To evaluate SDD feasibility, we will compare parental strain, quality of sleep and QoL during the non-exposure period and exposure period [22]. Based on a survey after the exposure period, we will calculate retention rate.

After the exposure period, we will offer the parents/guardians and children ≥12 years of age two options, based on the diagnostic performance of the NightWatch in their child.

- 1. In case of bad performance, we will offer a second-2-month period of monitoring in case we noted that an individualized adjustment of the algorithm (i.e. threshold adjustments for heart rate & accelerometry settings) using the data from the exposure period results in a substantial improvement. We will prospectively test the diagnostic performance of the adjusted algorithm prospectively and compare results between both periods.
- 2. In case of good performance, we will offer the parents/guardians the possibility to keep the NightWatch for further use, under certain conditions. (See 11.4 Ethics)

[figure not shown]

Figure 1: Study design.

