# **Limited-efficacy testing**

The parameter *Limited-efficacy testing* is defined as:

The extent in which the NightWatch shows a promise of being successful on key intermediate variables (quality of life, stress, sleep, and strain) in people with epilepsy and their parents/guardians.

Focusing on Intended effects of the NightWatch on key intermediate:

- Health-related QoL in people with epilepsy and their parents/guardians, including EQ-5D-5L [27] (Survey T0 and T2)
- Strain and sleep, including Caregiver Strain Index (CSI) [28] and Pittsburgh Sleep Quality Index (PSQI) [29] (Survey T0 and T2).

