# Run in period

During the first two months, there will be no home-based monitoring. Parent(s)/representative(s) will complete the questionnaires and a subgroup will be interviewed.

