#### Intervention

After two months, the researcher will visit the home to install the equipment. A camera and microphone will be placed on a pole, secured between floor and ceiling, next to the subject's bed. A suitcase containing a MacBook laptop and an external hard drive for data storage will be placed in the subject's room. The subject will be instructed to wear the NightWatch bracelet every night around the upper arm. When NightWatch is removed from its docking station, it will start running automatically. All recorded data (NightWatch, video and audio) will be stored automatically to the

MacBook and copied on hard drive. The researchers will replace the hard-drive every 2 weeks and store all recordings safely at SEIN or Kempenhaeghe for analysis. During the first weeks, the hard drive will be switched more often, in order to detect systematic errors in time.

In the morning, NightWatch must be connected to the docking station, when this happens, recordings stop automatically. During the study, subjects (or parent(s)/guardian(s)) do not have to switch any on/off button for the recordings. When NightWatch detects a seizure, it generates an alarm to the alarm station part of the NightWatch system at the parent(s)/guardian(s) bedroom. When the alarm goes off, the responding parent/guardian will check on their child and act upon the situation. He/she will keep a diary of all events. The SDD intervention period will last two months.

In case of technical problems, parent(s)/guardian(s) can contact the technical trial coordinator. If the parent(s)/guardian(s) give their consent, the coordinating investigator will be able to look into the study Macbook at their home from a distance true a secured program to solve technical problems. If the problem is not solved, the technical trial coordinator will visit the participant's home.

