#### 10.3 Other study parameters

Economic evaluation NightWatch

This economic evaluation will involve a combination of a cost-effectiveness analysis (CEA) and a cost-utility analysis (CUA). Additional costs and additional outcomes will be compared before and after implementation of NightWatch in a family home.

In the CEA, effects are presented in clinical outcomes and the incremental cost-effectiveness ratio (ICER). The primary outcomes measure for the cost-utility analysis will be QALYs, based on the EuroQol utility scores.[33]

We will assess intervention costs, healthcare costs, patient and family costs, and costs outside the health care sector. We have developed an adjusted version of the Medical Consumption Questionnaire (MCQ) and the Productivity Costs Questionnaire (PCQ) especially designed for parents or representatives of children with epilepsy. The valuation of healthcare costs, patient and family costs will be based on the updated Dutch manual for cost analysis in healthcare research. This manual recommends using standardized cost prices.[34]

A baseline analysis will be performed to examine the comparability of groups at baseline for both costs and outcomes. If necessary, methods will be applied to control for differences in base. To investigate whether data are normally distributed a Kolmogorov-Smirnov test will be performed. Depending on the results either parametric (t-tests) or bootstraps will be used. The uncertainty of the Increment Cost Effectiveness Ratio (ICER) will be checked by non-parametric bootstrapping. The bootstrapped cost-effectiveness ratios will be subsequently plotted in a cost-effectiveness plane. The choice of treatment depends on the maximum amount of money that society is prepared to pay for a gain in effectiveness, which is called the ceiling ratio. Therefore, the bootstrapped ICERs will also be depicted in a cost-effectiveness acceptability curve showing the probability that NightWatch is cost-effective using a range of ceiling ratios. Additionally, to demonstrate the robustness of our base-case findings a multi-way sensitivity analyses will be performed.

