# 11.4 Benefits and risks assessment, group relatedness

Implementing SDD is not considered to pose any substantial risks. Study participation can be a burden for the family (especially the parents/guardians) though, due to impact of the devices on privacy, impact of false alarms and time spent on the questionnaires &

interviews. Participation does, however, also offer better insight for the parents/guardians in the actual nocturnal seizure activity of their child, demonstrates the added value of the NightWatch and may help them to timely alert to a major seizure. When actual seizure activity is not consistent with the parent's expectations, this information can be confronting. All study results will be shared with the attending neurologists, so parents/guardians will be able to discuss this problem.

We will inform subjects and parent(s)/guardian(s) as good as possible on the impact of the study design on their privacy. It can be quite a burden to have a camera running in your (child's) room every night. To minimize this burden, we will give the subject and parent(s)/guardian(s) the opportunity to delete sensitive video or audio material from the storage data before it is send to the researchers. To prevent the risk of data getting lost, we do not allow subjects or parent(s)/guardian(s) to delete the material themselves. Every 1-2 weeks, when a trial nurse comes to their home to switch the external hard disk for an empty one, they are able to delete any footage they want, without any consequences. If subjects of parent(s)/guardian(s) do not want the trial nurse to see or hear the sensitive material, they can simply refer to a specific night, or time-window during a night, which will then be deleted by the trial nurse. If they wish to stop the recordings, they can contact the researcher to discuss which recordings should be stopped and those will be switched off immediately.

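### The T0–T2 changes and the ICER are credited to NightWatch alone, but the exposure period also brings in home video and audio recording and study visits

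*Combined protocol and SAP*

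**What the plan says.** The comparison is within families. Section 3 states that "we will compare parental strain, quality of sleep and QoL during the non-exposure period and exposure period". On the comparator, 8.3 (Run in period) says "During the first two months, there will be no home-based monitoring". On the exposure period, the Summary lists "Two months of nocturnal seizure monitoring at home, using NightWatch and the remote SDD".

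Section 8.3 (Intervention) describes what is installed besides NightWatch: "A camera and microphone will be placed on a pole, secured between floor and ceiling, next to the subject's bed", and "A suitcase containing a MacBook laptop and an external hard drive for data storage will be placed in the subject's room". It has the hard drive replaced every two weeks, more often at first; 11.4 has a trial nurse visiting the home every one to two weeks for this purpose. Under section 3 the video and audio marks are seen only by researchers and do not alert the family.

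The resulting change is attributed to the device. The limited-efficacy domain in 8.1.2 reads "Focusing on Intended effects of the NightWatch on key intermediate" variables, and 10.3 says "Additional costs and additional outcomes will be compared before and after implementation of NightWatch in a family home". The notes to Table 1, however, define T0 and T2 as before and after implementation of the SDDs, in the plural.

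**The concern.** A family that later buys NightWatch has neither the study camera nor the nurse visits. If the CSI, PSQI and EQ-5D-5L changes are read as NightWatch effects, the effect of the research recording is read with them. Section 11.4 itself expects such an effect: "It can be quite a burden to have a camera running in your (child's) room every night". Sections 11.4 and 12.2 both list privacy and false alarms as distinct burdens, but the outcome scores merge them.

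The bias could run either way. Recording that adds strain or disturbs sleep would hide a NightWatch benefit; regular contact with a study team that reassures parents would mimic one. The result therefore cannot be called conservative. The QALYs in 10.3 rest on EuroQol utilities, so the cost-utility result carries the same ambiguity. Time spent on study visits might also be counted as a cost of NightWatch.

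**Working it through.** **Step 1. What differs between the two periods**

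| Component | Usual care | Exposure | Source |
|---|---|---|---|
| Seizure diary | yes | yes | section 3 |
| NightWatch with alarm to parents | no | yes | 8.3 |
| Bedside camera and microphone | no | yes | 8.3 |
| Laptop case in child's room | no | yes | 8.3 |
| Disk-change visits | none described | every 1–2 weeks | 8.3, 11.4 |

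The diary runs in both periods and does not confound. The other four components start together. There is no control group (8.2), and no period or subgroup is planned with one component and not the others.

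**Step 2. Number of visits.** Taking two months as 61 days, 61/14 = 4.4 and 61/7 = 8.7, so roughly 4 to 9 visits per family plus installation. The upper end assumes weekly visits throughout. Section 8.3, with two-weekly changes after the first weeks, points nearer the lower end.

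**Step 3. Planned analysis.** Section 10.2 gives a paired t-test, and Table 3 gives repeated-measures ANOVA for PSQI. Neither has a term for the recording. The multi-way sensitivity analysis in 10.3 is not specified.

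**Step 4. The plan's own figure.** The only calculated sample size is 384 (4.4). It reproduces as 1.96² × 0.5 × 0.5 / 0.05² ≈ 384, but it concerns diagnostic performance. No effect size, SD or power is stated for the T0–T2 comparison, so no stated figure is contradicted here.

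**Step 5. Sensitivity, on assumed values.** Pairs: 60 × (1 − 0.30) = 42, from the drop-out allowance in 4.4. Assumptions: two-sided alpha 0.05, paired t-test, effects in units of the SD of change. Power comes from the noncentral t with 41 degrees of freedom and noncentrality (NightWatch effect + recording effect) × √42. The effect detectable with 80% power is 0.44 SD.

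| Recording effect (SD) | Chance of a significant change if NightWatch does nothing | Power for a 0.45 SD benefit, recording opposing | Same, recording reinforcing |
|---|---|---|---|
| 0 | 5% | 81% | 81% |
| 0.1 | 10% | 60% | 94% |
| 0.2 | 24% | 35% | 98% |
| 0.3 | 48% | 16% | 99.7% |

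For scale, if the SD of change on the 13-item CSI were 3 points (assumed), 0.2 SD would be 0.2 × 3 = 0.6 points. The table shows how sensitive the result is. It does not estimate the actual bias.

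**Step 6. Can a split by reported burden separate the parts?** Suppose the recording has no effect at all, the SD of CSI change is 3, and burden reported at T2 correlates 0.2 with the change because strained families report more burden of any kind. Under normality, a median split on burden gives a gap between groups of 2 × 0.798 × 0.2 × 3 = 0.96 points. At a correlation of 0.3 the gap is 2 × 0.798 × 0.3 × 3 = 1.44 points. Both exceed the 0.6 points above, so the split would manufacture a recording effect.

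**The case against.** The strongest reply is that the bundling is unavoidable. Under section 3, expert review of the video is the gold standard for the primary endpoint, and video is also used to screen for missed seizures. A reader might infer that the recording should be dropped or that the design is unsound; the documents do not support that.

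The aim is also modest. Limited-efficacy testing looks for promise within a six-domain feasibility study, section 3 speaks of SDD feasibility, and the T0 and T2 definitions already bracket all the SDDs. For feasibility, then, much of the problem is inconsistent labelling. The objection is weaker for the economic evaluation, which names NightWatch alone.

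A reader might further infer that no questionnaire item separates the two sources, or that study visits do inflate the PCQ. Neither can be shown. The T2 survey, the interview guide and the adjusted MCQ and PCQ are named but not reproduced. Only the absence of a planned separating analysis is visible. The text also does not say whether the equipment is still installed when T2 is completed.

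Families can have footage deleted or recordings switched off (11.4, 12.2), which may lessen the burden. No analysis uses this, so it does not separate the effects.

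**Conclusion.** The point stands as one of attribution in the secondary and economic results. The plan measures change under NightWatch plus home recording plus study visits, and reports it in 8.1.2 and 10.3 as the effect of NightWatch. This rests on the text and needs no numerical assumption. The size and direction of any recording effect are unknown, and the power figures depend wholly on assumed standardised effects and 42 analysable pairs.

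Two stronger conclusions would be wrong. The primary diagnostic endpoints are not touched. And naming the package does not turn the contrast into a causal estimate of the package: without a control group, time trends and regression to the mean remain. This is a cheap improvement that changes what the strain, sleep, quality-of-life and cost results can be said to show.

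**What to change.** 1. In 8.1.2, 10.2 and 10.3, describe the T0–T2 contrast as an uncontrolled before-after change under NightWatch together with home recording and study visits. Do not report it, or the ICER, as the effect of NightWatch alone.
2. In the existing T2 survey, ask the questions on positive and negative effects twice: once for NightWatch (wearing it, alarms) and once for the camera, microphone and visits. Report the answers descriptively. Do not split the T0–T2 change by burden reported at T2, since that conditions on a report made after the outcome.
3. Unless the adjusted MCQ and PCQ already do so, tell respondents at T2 to leave out time and costs caused only by study visits, recording equipment and questionnaires.

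The cost is wording in three sections, a few survey questions and one instruction line, or about a minute or two per respondent. The claim becomes more modest, and the two sources are described but still not causally separated. No extra participants or procedures are needed, and the recording stays as planned.

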#### 1. INTRODUCTION AND RATIONALE

Epilepsy impacts ~180.000 people in the Netherlands [1]. Despite advances in treatment, one third of all people with epilepsy continue to have seizures [2] that adversely affect quality of life (QoL) [3,4]. Poor seizure control is the major determinant of impaired QoL. Seizures impact not only individuals with epilepsy but also their guardians [5-7] as seizures are (1) unpredictable, (2) may cause loss of control and (3) cause life threatening situations, including injuries, status epilepticus and sudden unexpected death in epilepsy [8]. Convulsive seizures carry the greatest mortality risk, particularly those occurring at night, as these are often unwitnessed [9]. Childhood epilepsy has also a severe impact on parental QoL [10] and monitoring devices can help to improve parental anxiety levels, quality of sleep, and QoL [11]. Various non-EEG based signals have been assessed for the detection of potentially dangerous seizures [12]. Seizure detection devices (SDDs) have had, however, limited impact on epilepsy care so far. Barriers to SDD implementation include lack of external validation and high rate of false alarms. Most SDDs rely on a single modality. This approach likely explains limited sensitivity and specificity [12]. Previous studies validated multimodal algorithms for wearable sensors (accelerometry & heart rate) and demonstrated the feasibility of remote sensors (audio & video) to detect seizures [13-17]. Preliminary results indicate that the performance of the NightWatch is superior to a commonly used bed sensor, the Emfit. Our multicenter prospective trial in a residential population of adults with epilepsy and learning disabilities (LICSENSE trial, NTR4115) shows a median sensitivity per person of 85.7% with a positive predictive value of 49.3% and a median false negative alarm rate of 0.04 per person per night [18]. The interim analysis of our recent trial in 21 children (LICSENSE phase III) indicated that the algorithms needed an adjustment as in children higher heart rates are more common and less specific features for epilepsy appear thus increasing the number of false alarms. In response we updated our algorithm (with less emphasis on heart rate changes and more weight on movement changes). This approach still reach 80% sensitivity and 50% PPV in the majority (80%) of subjects (adults and children). This current prospective home-based trial is needed as a final validation step for the new algorithm in children and to evaluate feasibility of NightWatch. Former trials were performed without actual alarms. The current trial also enables us to get insight in the real life situation of children and their parents/guardians by focusing on feasibility. The literature has so far only discussed these needs with questionnaires but without insight into the home situation [19].

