#### 3. STUDY DESIGN

This is a home-based medical device intervention study, with prospective validation of our wearable device, including 60 children with refractory epilepsy (≥1 major nocturnal seizure per week) from three epilepsy centers (SEIN, Kempenhaeghe, UMCU). Subjects will receive usual care during the first two months (non-exposure period), followed by home-based nocturnal monitoring for two months (exposure period) [See Figure 1]. In both periods parents/guardians will be invited to keep a seizure diary. The NightWatch wirelessly transmits sensor outputs to a monitor in the parents/guardians room to alert them in case of a suspected seizure [See Figure 2]. Simultaneous video and audio recordings will be stored and analyzed offline.[21] Both algorithms will generate marks in dataflow, but these marks will not be used to alert the parents/guardians and will only be examined by the researchers.[See figure 3] The video material will also be used to screen for false negative alarms and to improve the algorithm when necessary (comparable with the LICSENSE study design, NTR4115).

Trial nurses will check the validity of the generated alarms and marks in a blinded way and screen 5% of the nocturnal video recordings without alarms. The LICSENSE trial demonstrated a median false negative alarm rate (FNAR) of 0,03 per subject per night with 10% screening of all nights. We believe that 5% screening will also be feasible, but we will perform an interim analysis after inclusion of 20 subjects to see whether FANR is still reasonably low (below 0,1 per night). If this is not the case, we will increase screening to 10% of all nights. The LICSENSE trial found a high Cohen's kappa (0.77) for inter-observer agreement between trial nurses and neurologists. Therefore, this expert review of the nocturnal video recordings by the trial nurses will serve as the gold standard. Cases of doubt will be discussed with a neurologist. Seizures will be stratified according to type (tonic-clonic, >30 seconds tonic, hyper motor and major) and severity (minor/major).

Parents/guardians will be invited to articulate their user experiences at focus meetings. Video tracings of detected seizures of their child will be shown to the parents/guardians who will be asked to indicate whether they would want to be alerted for these events or not. Results from these meetings will be included in the discussion on which type of seizures should be alarmed by SDDs.

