# 4.4 Sample size calculation

If 60 subjects are monitored for two months at minimal seizure frequency of 1 per week we will likely obtain around 540 seizures. To assess the diagnostic performance of the NightWatch this sample size seems sufficient. The detection algorithms aim to reach a sensitivity of 80% and a PPV of 50%. A sample size of 384 would be sufficient to reach a confidential interval of 5% (given a confidence level of 95%) [24]. A sample size of 60 subjects will allow us to intercept a drop-out rate of approximately 30% for the feasibility study.

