# 3. Economic evaluation of NightWatch

To evaluate the costs and effectiveness/utility of NightWatch for children and their parents/guardians from a societal perspective.

- Medical Consumption Questionnaire (MCQ) adjusted version (T0 and T2)
  - Questions regarding the subject (to be completed by one or two parent(s)/guardian(s) together)
  - Questions regarding the parent/guardian (to be completed by one or both parent(s)/guardian(s) separately)
- Productivity Costs Questionnaire (PCQ) adjusted version (T0 and T2)
  - To be completed by one or two parent(s)/guardian(s) separately.
- 4. Other secondary study parameters are:
- Compliance as indicated by frequency of use, i.e. hours per night that NightWatch is 'on'.
- Number and nature of interventions due to alarms.
- Effect of algorithm tailoring on performance of the NightWatch.

Table 1: Time schedule of surveys, questionnaires and interviews and feasibility domains.

Time			
period	Method	Duration	Topic
ТО	Surveys T0	10 minutes	
 
Personal/medical information subject and family (baseline)
 
MCQ and PCQ
 
Acceptability:
 
Intent to continue use;
 
Expectations Demand
 
Perceived demand
 

	Questionnaires	30 minutes	Limited-efficacy testing - CSI: Parental strain/stress - PSQI: Parental quality of sleep - EQ-5D-5L: Parental and child quality of life
T1	Diary		Demand - Actual use Implementation - Degree of execution
	Interview (subgroup)	60 minutes	Acceptability - Satisfaction Demand - Actual use Implementation - Degree of execution - Success or failure of execution - Amount, type of resources needed to implement Practicality - Factors affecting implementation ease or difficulty - Positive/negative effects on patients with epilepsy and their family members - Ability of parents/guardians to carry out intervention activities
T2	Surveys T2	10 minutes	
 
MCQ and PCQ         Acceptability
 
Satisfaction         Implementation
 
Degree of execution
 
Success or failure of execution
 
Amount, type of resources needed to implement         Practicality
 
Factors affecting implementation ease or difficulty
 
Positive/negative effects on patients with epilepsy and their parents/guardians
 
Ability of parents/guardians to carry out intervention activities
 

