#### **Optional phase**

Depending on the performance of NightWatch, parent(s)/guardian(s) will have different options. In case of bad performance, the researchers will offer them a second-2-month period of monitoring if an individually tailored adjustment of the algorithm could substantially improve performance. In case of good performance.

researchers we will offer the parent(s)/guardian(s) the possibility to keepNightWatch for further use. They can buy NightWatch at a 50% reduced rate of €750,-.

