In case of bad performance, we will assess whether better performance can be obtained using a tailored algorithm. To this end we will review all trial data of the participant and evaluate the effects of altering the algorithm thresholds. If this is likely to result in a substantial improvement, we will offer participants a second 2-month intervention period with a tailored NightWatch algorithm. At the end of this trial we will once again share the results with the family and the treating neurologist. If the performance has improved we will offer the NightWatch at reduces rate of € 750,-.

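### The effect of tailoring is judged as a change from a first period in which children were selected for bad performance, so regression to the mean favours tailoring on the selection measure

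*Combined protocol and SAP*

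**What the plan says.** Section 3 makes the second two-month period depend on how NightWatch performed in the individual child. It is offered after bad performance, if adjusting the heart-rate and accelerometry thresholds on the exposure-period data gives a substantial improvement. Section 8.3 (Optional phase) repeats the rule: "the researchers will offer them a second-2-month period of monitoring if an individually tailored adjustment of the algorithm could substantially improve performance". Section 11.4 describes the retrospective check: "To this end we will review all trial data of the participant and evaluate the effects of altering the algorithm thresholds".

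For the second period, Section 3 states: "We will prospectively test the diagnostic performance of the adjusted algorithm prospectively and compare results between both periods". Section 8.1.2, item 4, lists "Effect of algorithm tailoring on performance of the NightWatch" among the other secondary parameters.

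The readable text gives no numerical cut for bad performance or for substantial improvement, and does not say which performance measure decides. Section 8.2 describes no control. Section 10.1 provides for descriptive statistics on algorithm performance, and nothing in Section 10 is specific to tailoring.

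**The concern.** The two periods are not on an equal footing. The first-period result decides who enters the comparison; the second-period result does not. A child's observed sensitivity over a handful of seizures is partly chance, and children picked because it was low will on average do better next time with the same device and thresholds. The comparison in Section 3 assigns that rebound to tailoring.

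Testing the adjusted thresholds on new data is sound and protects the stand-alone second-period estimate from over-fitting. It does not repair the first-period reference. Tailored versus fixed also coincides completely with second versus first period, so any change over time in seizures or sleep enters the same contrast.

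At stake is the only out-of-sample comparison the plan names for the tailoring effect. It could credit individual adjustment with a gain that an unchanged algorithm would also show on average.

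**Working it through.** **Inputs from the plan.** Section 4.4 expects about 540 seizures from 60 children over two months at one per week. This reproduces as 60 × 9 weeks × 1 = 540, or 540/60 = 9 seizures per child at the eligibility minimum. The same section gives targets of 80% sensitivity and 50% PPV. The plan gives no figure for the tailoring comparison.

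**Assumptions.** Mean sensitivity m = 0.80; bad means observed first-period sensitivity below 0.80; intra-child correlation (ICC) 0.05 to 0.4, extended to 0.6 and 0.8; n = 9, 20 or 36 seizures per child per period; no true effect of tailoring. The second entry condition (apparent gain on re-tuning) is not modelled.

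**Model.** Each child's true sensitivity p follows Beta(mk, (1−m)k) with k = 1/ICC − 1. Detected seizures X1 and X2 in the two periods are independent Binomial(n, p). Because E[X2/n | X1 = x] = (mk + x)/(k + n), the expected change among selected children is

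gain = (m − s) × k/(k + n),

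where s is the mean first-period sensitivity of the selected children. Selecting on a low value makes s < m, so the gain is positive for any such cut.

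**Hand check without between-child variation (ICC 0, n = 9).** Selection means at most 7 of 9 detected.
- P(9) = 0.8^9 = 0.134 and P(8) = 9 × 0.8^8 × 0.2 = 0.302, so 56.4% are selected.
- s = (7.2 − 9 × 0.1342 − 8 × 0.3020)/(0.5638 × 9) = 0.705.
- The second-period expectation is 0.80, so the gain is 9.5 points.

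**Worked cases with between-child variation.**
- n = 9, ICC 0.05: k = 19, s = 0.679; 0.121 × 19/28 = 0.082.
- n = 9, ICC 0.2: k = 4, s = 0.606; 0.194 × 4/13 = 0.060.
- n = 9, ICC 0.4: k = 1.5, s = 0.504; 0.296 × 1.5/10.5 = 0.042.
- n = 36, ICC 0.2: k = 4, s = 0.603; 0.197 × 4/40 = 0.020.

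Expected apparent gain in sensitivity, percentage points, with no true effect:

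| Seizures per child | ICC 0.05 | 0.1 | 0.2 | 0.4 | 0.6 | 0.8 |
|---|---|---|---|---|---|---|
| 9 | 8.2 | 7.3 | 6.0 | 4.2 | 2.9 | 1.6 |
| 20 | 6.4 | 5.0 | 3.6 | 2.3 | 1.5 | 0.7 |
| 36 | 3.6 | 2.8 | 2.0 | 1.2 | 0.8 | 0.4 |

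For ICC 0.05 to 0.4 this cut selects 32% to 53% of children.

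**Check of the remedy.** Second-period data play no part in selection or tuning, so a comparison of both algorithms on those data has expectation zero when tailoring does nothing. With 400,000 simulated children per setting (n = 9, 20, 36; ICC 0.05, 0.2, 0.4), the planned contrast reproduced the gains above. The paired second-period contrast stayed within 0.0006 of zero in all nine settings.

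**Seizures missed by both algorithms.** Section 3 has nurses review the alarms and the video and audio marks, and "screen 5% of the nocturnal video recordings without alarms"; Section 8.3 adds a parent diary. In the worst case only the 5% screen finds a seizure that both NightWatch versions miss. If a share q of true seizures is missed by both, the counted denominator is (1 − q) + 0.05q = 1 − 0.95q of the true one, and the paired sensitivity difference is inflated by 1/(1 − 0.95q). That is 1.05, 1.10 and 1.23 for q = 5%, 10% and 20% (assumed shares). The sign cannot change, because such seizures count equally for both versions.

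**The case against.** Tailoring appears in neither the primary nor the secondary objectives. It is the last bullet of the other secondary parameters, in an optional phase for a few children, with no test or success criterion and descriptive reporting. That stands, and limits the weight of the point. A descriptive before-after difference will still be read as the effect of tailoring, and the remedy is one sentence.

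The plan also contains a same-data comparison: altered thresholds are evaluated on the child's own first-period recordings. This is an in-sample entry check and therefore optimistic, but it exists, so it would be wrong to say that the between-period change is the only comparison of any kind. Nor does Section 3 exclude re-running the fixed algorithm on second-period data; it simply does not plan it.

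The ICC has no source in the plan. Tailoring presupposes stable differences between children, which argues for high values, and there the bias is small. This stands and is why the table extends to 0.8.

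A reader might infer larger figures from Section 1, where 80% of subjects are said to reach the targets. Setting the share below 80% sensitivity to 20% would give 5.1 to 12.7 points at 9 seizures. But that statement covers sensitivity and PPV jointly, in adults and children together, and does not say how many fail on sensitivity. The paediatric problem that Section 1 reports is false alarms, so bad may often mean low PPV or many alarms.

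**Conclusion.** The point holds in limited form. Regression to the mean biases the planned between-period change upward in expectation on the measure or measures used for selection. Only this component has a firm direction. A measure not used for selection may show little or none of it, the confounding with time has unknown sign, and in a small group a single comparison could go either way.

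The size is illustrative. Under the stated assumptions it is 4.2 to 8.2 points of sensitivity at 9 seizures per child, 2.3 to 6.4 at 20 and 1.2 to 3.6 at 36 for ICC 0.05 to 0.4. It falls to 2.9–1.6, 1.5–0.7 and 0.8–0.4 points for ICC 0.6–0.8. Bias in PPV or false alarm rate is not quantified here.

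A reader might infer that every performance measure is inflated, or that the trial's main result is compromised. The documents support neither. The primary analysis uses the fixed algorithm in the first exposure period, before this selection. The stand-alone second-period estimate and the device-offer rule in Section 11.4 are also unaffected.

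**What to change.** In Section 3, replace the second half of the sentence on testing the adjusted algorithm by: *run the original fixed algorithm offline on the stored period-2 sensor data and compare it with the tailored algorithm on the same period-2 nights, paired within child (sensitivity, PPV, false alarm rate), with the marks of both reviewed without labels showing which algorithm produced them and all confirmed seizures in the denominator for both.*

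Name this paired difference as the tailoring effect in Section 8.1.2, item 4. Report the change from the first period as descriptive only. Leave the device-offer rule in Section 11.4 as it is.

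Cost: no new patients, visits or devices, provided the second period stores data as Section 8.3 describes for the first ("All recorded data (NightWatch, video and audio) will be stored automatically"). Re-evaluating thresholds on recorded data is already part of the plan. The added work is nurse review of the fixed algorithm's additional marks in the few second-period children.

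Limits: blinding of the review stays incomplete, because only the tailored algorithm's alarms sound and parents respond on camera. Seizures that no source finds leave both absolute sensitivities too high and inflate the paired sensitivity difference, at most by the worst-case factors shown in the working.
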